After review of initial feasibility and power analyses, complete creation of the remaining covariates (see Table 1 below for list of covariates). Again, using the dummy outcome of a 90-day gap in database enrollment, complete a 1:1 PS-matched analysis. The PS should include the complete list of covariates (excluding laboratory values, which are missing in some patients).

- Provide plot of PS distributions stratified by treatment group.

Note- Please refer to **Appendix B**.

- Report covariate balance after matching.

Note- For Table 1, please refer to **Appendix B**.

- Report reasons for censoring by treatment group.

	Overall	Referent	Exposure
Dummy Outcome	0 (0.00%)	0 (0.00%)	0 (0.00%)
Death	1,879 (1.83%)	946 (1.84%)	933 (1.82%)
Start of an additional exposure	3,238 (3.15%)	1,642 (3.20%)	1,596 (3.11%)
End of index exposure	71,983 (70.13%)	36,022 (70.19%)	35,961 (70.07%)
Specified date reached (Dec 17/Dec 18/Dec 19)	6,822 (6.65%)	3,196 (6.23%)	3,626 (7.07%)
End of patient enrollment	5,237 (5.10%)	2,408 (4.69%)	2,829 (5.51%)
Switch to other NOACs (for censoring) + nursing home admission	13,477 (13.13%)	7,104 (13.84%)	6,373 (12.42%)

- Report follow-up time by treatment group.

Median Follow-Up Time (Days) [IQR]			
Patient Group	Optum	Truven	Medicare
Overall Patient Population	98 [38-209]	98 [44-236]	98 [38-206]
Referent	98 [38-190]	98 [44-192]	98 [38-188]
Exposure	98 [38-231]	119 [44-281]	98 [38-228]

- Report overall risk of the primary outcome.

	Optum	MarketScan	Medicare	Pooled
Risk per 1,000 patients	7.00	7.33	12.05	10.08

10. Final Power Assessment

Date conducted:

- Re-calculate power in the appropriate excel table, using the revised number of matched patients from the PS-match in Section 9. All other parameters in the table should be the same as in Section 8.

- For rivaroxaban vs. warfarin

- Pooled

Superiority Analysis		Non-inferiority Analysis	
Number of patients matched	102,636	Number of patients matched	102,636
Reference	51,318	Reference	51,318
Exposed	51,318	Exposed	51,318
Risk per 1,000 patients	10.08	Risk per 1,000 patients	10.08
Desired HR from RCT	0.79	Assumed HR from RCT	1
Alpha (2-sided)	0.05	Alpha (2-sided)	0.05
		Non-inferiority margin	1.46
Number of events expected	1034.57088	Number of events expected	1034.57088
Power	0.966450516	Power	0.999981559

o Optum

Superiority Analysis		Non-inferiority Analysis	
Number of patients matched	17,900	Number of patients matched	17,900
Reference	8,950	Reference	8,950

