Exposed	8,950	Exposed	8,950
Risk per 1,000 patients	7.00	Risk per 1,000 patients	7.00
Desired HR from RCT	0.79	Assumed HR from RCT	1
Alpha (2-sided)	0.05	Alpha (2-sided)	0.05
		Non-inferiority margin	1.46
Number of events expected	125.3	Number of events expected	125.3
Power	0.261393559	Power	0.562809862

o MarketScan

Superiority Analysis		Non-inferiority Analysis	
Number of patients matched	22,600	Number of patients matched	22,600
Reference	11,300	Reference	11,300
Exposed	11,300	Exposed	11,300
Risk per 1,000 patients	7.33	Risk per 1,000 patients	7.33
Desired HR from RCT	0.79	Assumed HR from RCT	1
Alpha (2-sided)	0.05	Alpha (2-sided)	0.05
		Non-inferiority margin	1.46
Number of events expected	165.658	Number of events expected	165.658
Power	0.329138572	Power	0.682759594

- Medicare

Superiority Analysis		Non-inferiority Analysis	
Number of patients matched	62,136	Number of patients matched	62,136
Reference	31,068	Reference	31,068
Exposed	31,068	Exposed	31,068
Risk per 1,000 patients	12.05	Risk per 1,000 patients	12.05
Desired HR from RCT	0.79	Assumed HR from RCT	1
Alpha (2-sided)	0.05	Alpha (2-sided)	0.05
		Non-inferiority margin	1.46
Number of events expected	748.7388	Number of events expected	748.7388
Power	0.897079133	Power	0.999353731

- Stop analyses until balance and final power assessment are reviewed by primary investigators, FDA, and assigned members of advisory board.

Reviewed by PI:	[name]	Date reviewed:	9/8/20
Reviewed by FDA:	[name]	Date reviewed:	9/29/20
Reasons for stopping analysis (if required):			

11. Study Confidence and Concerns

Deadline for voting on study confidence and listing concerns:

Date votes and concerns are summarized:

- If final feasibility and power analyses are reviewed and approved, proceed to the remaining protocol steps.

- All study team and advisory board members that review this protocol should at this stage provide their level of confidence for the success of the RWD study in the [Google Form](#). This form also provides space for reviewers to list any concerns that they feel may contribute to a failure to replicate the findings of the RCT, including differences in study populations, poor measurement of study variables, or residual confounding. All responses will be kept confidential and individual-level results will only be shared with the individual respondent.
- After the deadline for voting has passed, provide the distribution of responses and summarize all concerns here.

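### Section 10: the pooled expected events (1,034.57) do not equal the sum of the three database tables (1,039.70), and the outcome risks used have no stated denominator

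*Combined protocol and SAP*

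**What the plan says.** Section 9 (Balance Assessment) describes a 1:1 propensity-score-matched run with a dummy outcome and then asks the team to "Report overall risk of the primary outcome". The line that follows, in the order Optum, MarketScan, Medicare, pooled, reads "Risk per 1,000 patients 7.00 7.33 12.05 10.08". It gives no denominator and does not say whether the risks are from before or after matching.

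Section 10 (Final Power Assessment) updates the matched counts and adds: "All other parameters in the table should be the same as in Section 8". Its four tables carry "Number of patients matched 102,636" (pooled), "Number of patients matched 17,900" (Optum), "Number of patients matched 22,600" (MarketScan) and "Number of patients matched 62,136" (Medicare), each with the matching risk from Section 9. The superiority half uses "Desired HR from RCT 0.79". The non-inferiority half uses a true hazard ratio of 1 and a margin of 1.46. Alpha is 0.05 two-sided throughout.

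The matched runs in Sections 8 and 9 use the dummy outcome. The real primary endpoint is named as the outcome only in the Section 7 feasibility analysis, where no matching is described.

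**The concern.** The pooled cohort is the three matched database cohorts put together: 17,900 + 22,600 + 62,136 = 102,636. Its expected events should therefore be the sum of theirs, and they are not.

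Because the risks appear in the section on the matched cohort, beside matched censoring counts, a reader will take them as matched-cohort risks. If they are not, the tables describe the event yield of a different set of patients from the one to be analysed. The plan stops at this point until the investigators, the regulator and advisory board members have reviewed balance and power, so the figures should add up and their source should be clear.

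**Working it through.** **1. Reproduce the stated figures.** Inputs are the matched N, risk, hazard ratio, margin and alpha in Section 10. Expected events are E = N × risk / 1,000. Power is Φ(½·√E·|ln HR| − 1.96), with HR 0.79 for superiority and 1.46 for non-inferiority.

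| Table | N × risk / 1,000 | E stated | Superiority: computed / stated | Non-inferiority: computed / stated |
|---|---|---|---|---|
| Optum | 17,900 × 7.00 | 125.3 | 0.2609 / 0.2614 | 0.5628 / 0.5628 |
| MarketScan | 22,600 × 7.33 | 165.658 | 0.3289 / 0.3291 | 0.6828 / 0.6828 |
| Medicare | 62,136 × 12.05 | 748.7388 | 0.8971 / 0.8971 | 0.9994 / 0.9994 |
| Pooled | 102,636 × 10.08 | 1,034.57088 | 0.9665 / 0.9665 | 0.99998 / 0.99998 |

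Every table is arithmetically correct on its own inputs. The small superiority differences are the opposite tail, which the formula above omits.

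**2. Compare the pooled row with its parts.** 125.3 + 165.658 + 748.7388 = 1,039.6968. The gap is 1,039.6968 − 1,034.5709 = 5.13 events (0.5%). The implied pooled risk is 1,039.6968 / 102.636 = 10.13 per 1,000.

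**3. Can rounding explain it?** Let each risk vary by ±0.005. The database sum then lies between 1,039.18 and 1,040.21, and the pooled row between 1,034.06 and 1,035.08. The ranges do not meet.

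**4. Which cohort gives 10.08?** Weight 7.00, 7.33 and 12.05 by different cohort sizes:

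- Matched (17,900; 22,600; 62,136): 10.13.
- Unmatched, Appendix B, both arms (25,701 + 14,869 = 40,570; 32,295 + 17,748 = 50,043; 92,403 + 40,652 = 133,055): 2,254.12 / 223.668 = 10.078, which rounds to 10.08.
- Unmatched, Section 5.3 flowchart (40,604; 50,085; 133,230): 10.079, also 10.08.
- Unmatched rivaroxaban patients only (14,869; 17,748; 40,652), a proxy for a nearly complete three-covariate match in Section 8: 9.88.

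**5. Whole-event check.** In 17,900 patients, 125 events give 6.98 per 1,000 and 126 give 7.04, so none gives 7.00. In 22,600 patients, 165 give 7.30 and 166 give 7.35, so none gives 7.33. In the Appendix B unmatched cohorts, 284/40,570 = 7.00 and 367/50,043 = 7.33. For Medicare the check does not discriminate: 749/62,136 and 1,603/133,055 both give 12.05.

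**6. Power with a consistent pooled row.** √1,039.6968 = 32.244, and 32.244 / 2 × 0.23572 − 1.96 = 1.840, so superiority power is 0.9671. Non-inferiority power is 0.99998.

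**7. Range for the unknown matched risk (assumption).** If matched events were 20% lower or higher than 1,039.70 (832 to 1,248), pooled superiority power would be 0.925 to 0.986, with non-inferiority power above 0.9997. Superiority power would be 0.22 to 0.30 in Optum, 0.27 to 0.38 in MarketScan and 0.82 to 0.94 in Medicare.

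**The case against.** Carrying an overall, arm-blind risk forward is the plan's stated procedure and a legitimate planning choice. Each table is internally correct, and the discrepancy moves power by less than 0.001. All of this stands, and it limits the point to consistency and labelling. It does not explain why a total differs from its parts.

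The origin of the risks is also not documented. Above 100,000 patients some whole number fits any two-decimal risk, so the fits at 133,055 and 223,668 carry no weight on their own. The flowchart's Optum total does not fit either, since 284/40,604 is 6.99. What remains is the pooled weighting and the failure of the matched Optum and MarketScan counts. Together these make the unmatched source a strong inference, not a stated fact.

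A reader might go further and infer that the superiority powers are overstated: the unmatched cohort is 67.2% warfarin (150,399 / 223,668), while the matched cohort is 1:1 and the table assumes HR 0.79. Rescaling each database by ((1 + r)/2) / (p + r(1 − p)), with r = 0.79 and warfarin shares p of 0.633, 0.645 and 0.694, gives about 998 events and power 0.961. The documents do not support this. It requires the crude arm risks before matching to stand in the ratio 0.79, yet those arms are confounded and the risks are per patient over unequal as-treated follow-up. With r from 0.90 to 1.10 the same formula gives 1,020 to 1,058 events and power 0.964 to 0.969.

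Nor does case mix point only downward. From Appendix B, both arms combined, unmatched to matched:

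- any stroke: 43,540/223,668 = 19.5% to 21,028/102,636 = 20.5%;
- any hospitalization: 79,214/223,668 = 35.4% to 43,630/102,636 = 42.5%;
- oldest age band: 160,859/223,668 = 71.9% to 71,726/102,636 = 69.9%.

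**Conclusion.** The pooled table in Section 10 is inconsistent with its three database tables by 5.13 expected events, and rounding cannot account for it. On the plan's own database figures the pooled row should read 1,039.70 events and superiority power 0.9671. The one correction that can be demonstrated is therefore slightly upward. Non-inferiority power is unaffected in practice.

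That the risks come from the unmatched cohorts is inferred, assuming they are simple events per patient rounded to two decimals. The event count and power of the matched cohorts cannot be computed from the documents. The ±20% range above is an assumption, and neither direction is established. Section 10 sets no numerical power threshold, and no go/no-go conclusion would change.

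**What to change.** **Minimum.** In the pooled table of Section 10, set expected events to the sum of the databases (1,039.70; 10.13 per 1,000), superiority power to 0.9671 and non-inferiority power to 0.99998. In Section 9, state the cohort and denominator for each risk. This is a spreadsheet edit and a line of text.

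**Preferred.** Replace only the risk row with the overall primary-outcome risk counted, without splitting by arm, in the matched cohorts of 17,900, 22,600 and 62,136. Then restate events and power in all four tables, with the pooled events as the sum. Write this as an exception to the carry-forward sentence, for example: *The matched patient numbers and the overall outcome risk are updated; hazard ratio, alpha and non-inferiority margin stay as in Section 8.* Deleting that sentence altogether would also release the hazard ratio, alpha and margin shortly before outcome analysis.

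The preferred version costs one count per database. An arm-blind count respects the Section 7 bar on association measures and arm-specific rates. However, overall risks at two known arm mixes carry some confounded information on the arms, so the investigators and the regulator should agree to the count first. If they do not, the minimum fix is enough.

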14.1 Table 1: Baseline characteristics before and after adjustment

Variable	Before adjustment			After adjustment		
	Referent	Exposure	Std. diff.	Referent	Exposure	Std. diff.
Number of patients			-			-
Age categories						
...						

14.2 Table 2: Follow-up time

Patient Group	Median Follow-Up Time (Days) [IQR]
Overall Patient Population	
Referent	
Exposure	

14.3 Table 3: Censoring events

	Overall	Referent	Exposure
Outcome			
Death			
Start of an additional exposure			
End of index exposure			
Specified date reached			
End of patient data			
End of patient enrollment			
...			

14.4 Table 4: Results from primary analyses;

Analysis	No. exposed events	No. referent events	Exposed rate	Referent rate	HR (95% CI)
Crude					
Analysis 1					
Analysis 2					
...					

HR, Hazard Ratio; CI, Confidence Interval.

14.5 Table 5: Results from secondary analyses;

15. References

Appendix A

#	ROCKET-AF trial definitions	Implementation in routine care	References/Rationale	Color coding
	Trial details- Primary indication, 4a- Unintended S with label change HR = 0.79 (95% CI 0.66-0.96)		
Please see the following Google Drive for further details or any missing information: https://drive.google.com/open?id=1WDb18wvwIIfakell7cuK-VCmb6b-gV
	Criteria
			
ICD-10 codes are not listed in this document because of excel file size limitations and excessive number of ICD-10 codes. Full ICD-10 code lists will be available in the above Google Drive Folder (link above). ICD-9 to ICD-10 code conversions were completed using a SAS macro that implements forward/ backward mapping based on the CMS ICD-9 to ICD-10 mapping: https://www.ncbi.nlm.nih.gov/pmc/articles/PMC3070730/
	Adequate mapping in claims
		EXPOSURE vs. COMPARISON		
	Rivaroxaban vs. Warfarin	Rivaroxaban 20mg OR 15mg daily (if low GFR) vs. adjusted-dose warfarin		Intermediate mapping in claims
		PRIMARY OUTCOME		Poor mapping or cannot be measured in claims
	Primary endpoint of stroke (ischemic or hemorrhagic) and systemic embolism.	Measured 1 day after drug initiation in primary diagnosis position specified below and inpatient care setting: Stroke: ICD-9 discharge diagnosis codes: 430.xx Subarachnoid hemorrhage (SAH) 431.xx Intracerebral hemorrhage (ICH) 433.x1 Occlusion and stenosis of precerbral arteries with cerebral infarction 434.xx (excluding 434.x0) Occlusion and stenosis of cerebral arteries with cerebral infarction 436.x Acute, but ill-defined cerebrovascular events Systemic embolism: ICD-9 discharge diagnosis code: 444.xx Arterial embolism ICD-10 discharge diagnosis code: I74.x Arterial embolism and thrombosis	
For stroke: PPV of 85% or higher for ischemic stroke PPV ranging from 80% to 98% for hemorrhagic stroke →[Andrade SE, Harrold LR, Tjia J, et al. A systematic review of validated methods for identifying cerebrovascular accident or transient ischemic attack using administrative data. Pharmacoepidemiology and Drug Safety 2012;21 Suppl 1:100-28.] →[Tirschwell DL, Longstreth WT, Jr. Validating administrative data in stroke research. Stroke; a journal of cerebral circulation 2002;33:2465-70.] →[Roumali CL, Mitchell E, Gideon PS, Varas-Lorenzo C, Castellsague J, Griffin MR. Validation of ICD-9 codes with a high positive predictive value for incident strokes resulting in hospitalization using Medicaid health data. Pharmacoepidemiology and drug safety 2008;17:20-6.]
	Can't be measured in claims but not important for the analysis
		INCLUSION CRITERIA		
1	Men or women aged ≥18 years	Measured on the day of drug initiation: Age >=18		
2	Non-valvular Atrial fibrillation Atrial fibrillation must be documented by ECG evidence (e.g., 12-lead ECG, rhythm strip, Holter, pacemaker interrogation) within 30 days before randomization. In addition, subjects must have medical evidence of atrial fibrillation within 1 year before and at least one day before the qualifying ECG evidence. This could be obtained from a notation in the subject's record (e.g., medical chart, hospital discharge summary).	Measured 12 months prior to and including day of drug initiation, with >2 diagnoses separated by at least 14 days, in any diagnosis position and inpatient or outpatient care setting: Atrial fibrillation: ICD-9 diagnosis: 427.31 ICD-10 diagnosis: I48.0x, I48.1x, I48.2x, I48.9x		
3	Non-valvular Atrial fibrillation Subjects with newly diagnosed atrial fibrillation are eligible provided that: - there is evidence that the atrial fibrillation is non-valvular - cardioversion is not planned - there is ECG evidence on 2 occasions 24 hours apart demonstrating atrial fibrillation			
	For Inclusion Criteria 4 It is either A) History of ischemic stroke or TIA or arterial embolism -OR- B) 2 of the following 4 1) Heart failure 2) Hypertension 3) Age >=75 4) Diabetes			
4	History of prior ischemic stroke, TIA or non-CNS systemic embolism believed to be cardioembolic in origin	Measured any time prior to and including day of drug initiation in any diagnosis position and inpatient or outpatient care setting: Ischemic stroke: ICD-9 diagnosis: 433.x, 434. x, 436.xx TIA: ICD-9 diagnosis: 435.xx Systemic embolism: ICD-9 diagnosis: 444.xx	
Patorno, Elisabetta et al. "Cardiovascular outcomes associated with canagliflozin versus other non-gliflozin antidiabetic drugs: population based cohort study." BMJ 2018;360:k119 http://dx.doi.org/10.1136/bmj.k119
 
Patorno, Elisabetta et al. "Empagliflozin and the Risk of Heart Failure Hospitalization in Routine Clinical Care: A First Analysis from the Empagliflozin Comparative Effectiveness and Safety (EMPRISE) Study." Circulation. 2019 Apr 8. doi: 10.1161/CIRCULATIONAHA.118.039177
	
	OR 2 or more of the following risk factors	Measured anytime prior to and including day of drug initiation in any diagnosis position and inpatient or outpatient care setting:		
4a	– Heart failure and/or left ventricular ejection fraction ≤35%	Heart failure: ICD-9 diagnosis: 428.x, 398.91, 402.01, 402.11, 402.91, 404.01, 404.11, 404.91, 404.03, 404.13, 404.93	
Patorno, Elisabetta et al. "Cardiovascular outcomes associated with canagliflozin versus other non-gliflozin antidiabetic drugs: population based cohort study." BMJ 2018;360:k119 http://dx.doi.org/10.1136/bmj.k119
 
Patorno, Elisabetta et al. "Empagliflozin and the Risk of Heart Failure Hospitalization in Routine Clinical Care: A First Analysis from the Empagliflozin Comparative Effectiveness and Safety (EMPRISE) Study." Circulation. 2019 Apr 8. doi: 10.1161/CIRCULATIONAHA.118.039177
	

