5.1 Cohort Summary

This study will involve a new user, parallel group, propensity score-matched, retrospective cohort study design comparing rivaroxaban (at a daily dose of 20mg or 15 mg) to warfarin users. The patients will be required to have continuous enrollment during baseline period of 180 days before initiation of rivaroxaban or warfarin (index date). We will restrict the analyses to patients with a diagnosis of atrial fibrillation with risk factors for stroke or systemic embolism.

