5.2.1 Eligible cohort entry dates

Rivaroxaban was approved for non-valvular atrial fibrillation on November 4, 2011.

- For Marketscan: November 4, 2011 -December 31, 2018 (end of data availability).
- For Medicare: November 4, 2011 -December 31, 2017 (end of data availability).
- For Optum: November 4, 2011 -December 31, 2019 (end of data availability).

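### As printed, the ICD-10 wildcard I48.9x for atrial fibrillation also admits unspecified atrial flutter, which the ICD-9 code does not, so eligibility depends on coding era

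*Combined protocol and SAP*

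**What the plan says.** Section 5.1 sets the population: "We will restrict the analyses to patients with a diagnosis of atrial fibrillation with risk factors for stroke or systemic embolism". The trial criterion reproduced in Appendix A, inclusion 2, is stricter still: "Atrial fibrillation must be documented by ECG evidence". Flutter is not mentioned in either place.

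The claims implementation of inclusion 2 gives two code lists. The ICD-9 list is one fully specified code, "Atrial fibrillation: ICD-9 diagnosis: 427.31". The ICD-10 list is four wildcards, "ICD-10 diagnosis: I48.0x, I48.1x, I48.2x, I48.9x". The codes must appear within 12 months up to and including drug initiation, "with >2 diagnoses separated by at least 14 days, in any diagnosis position and inpatient or outpatient care setting". Inclusion 3 has no implementation of its own, and the Section 5.3 flowchart applies inclusions 2 and 3 as one step.

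Section 5.2.1 opens entry on 4 November 2011 in all three databases and closes it at the end of 2017 (Medicare), 2018 (MarketScan) and 2019 (Optum). The opening note of Appendix A says that complete ICD-10 lists are kept in an external folder and that ICD-9 codes were converted with a mapping macro.

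**The concern.** The two lists are meant to describe one condition, but they do not have the same scope. The ICD-9 list is closed. The ICD-10 list ends in an open wildcard which, in the classification the plan uses, contains a flutter code next to the fibrillation code.

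Two features of the printed text suggest that this was not intended. The flutter codes I48.3 and I48.4 are absent, and admitting unspecified flutter while leaving out typed flutter has no stated rationale. Where Appendix A wants a wildcard without one of its subcodes, it says so: the stroke outcome uses "434.xx (excluding 434.x0". Nothing similar is written under I48.9x.

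Two things are at stake. The first is fidelity to the trial population, because patients without the indication under study could enter. The second is consistency over time, because the entry rule would change when the coding system changed. Appendix B prints no calendar-year or index-date covariate, so the match does not directly balance coding era between the arms.

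**Working it through.** **1. Code lists side by side.** Code meanings are those of the standard classification; the document prints only the codes.

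| | ICD-9 list | ICD-10 list |
|---|---|---|
| Fibrillation | 427.31: listed | I48.0x, I48.1x, I48.2x, I48.91 (through I48.9x): listed |
| Typed flutter | no separate code | I48.3, I48.4: not listed |
| Unspecified flutter | 427.32 (all flutter): not listed | I48.92: taken in by I48.9x |

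**2. Trace one patient.** Take a patient with repeated flutter diagnoses at least 14 days apart within 12 months and no fibrillation code. Coded 427.32, the patient fails inclusion 2. Coded I48.92, the patient passes inclusion 2 as printed. No later criterion asks for a fibrillation code.

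**3. Share of each entry window under ICD-10.** Assume a switch on 1 October 2015, a date the document does not give. Share = days from the switch to the end of the window, divided by days from 4 November 2011 to the end of the window, both inclusive.

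- Optum: 1,553 / 2,980 = 0.521
- MarketScan: 1,188 / 2,615 = 0.454
- Medicare: 823 / 2,250 = 0.366

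**4. Illustrative count.** Assume also that entry is even over time and that a share p of ICD-10-era entrants qualifies only through I48.92. The document gives no value for p; 2% and 8% are used only to show a range. Count = p × Σ(N × share).

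- Matched patients (Section 10): 17,900 × 0.521 + 22,600 × 0.454 + 62,136 × 0.366, with unrounded shares, = 42,324. At 2% this is 846 and at 8% it is 3,386, that is 0.8% to 3.3% of 102,636.
- Final cohort before matching (Section 5.3): 40,604, 50,085 and 133,230, in total 223,919, give 92,647 ICD-10-era entrants. At 2% this is about 1,850 and at 8% about 7,400.

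**5. Conditional ceiling.** Appendix B has an atrial fibrillation covariate. Its codes and window are not stated. If it excludes flutter, patients without it cap flutter-only entry.

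- Unmatched: (150,399 − 145,029) + (73,269 − 71,467) = 5,370 + 1,802 = 7,172 of 223,668, or 3.2%.
- Matched: (51,318 − 49,913) + (51,318 − 49,864) = 1,405 + 1,454 = 2,859 of 102,636, or 2.8%.

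The 8% scenario exceeds both caps (7,400 against 7,172; 3,386 against 2,859). On the matched cap, p could be at most 2,859 / 42,324 = 6.8%. The cap is not firm, because a shorter window than the 12 months of inclusion 2 could equally explain a missing covariate.

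**6. Power after removing such patients.** Superiority power = Φ(½√D × |ln 0.79| − 1.96). With the pooled D = 1,034.57 of Section 10 this returns 0.9665, the plan's own figure. If events fall by 3.3%, in proportion to patients, D is about 1,000 and power about 0.96.

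**The case against.** The strongest reply has four parts.

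- *The decisive facts are external.* The document does not label the codes, name flutter or date the switch. This is true, and the point depends on the standard meaning of codes that the plan itself chose. That is a definition rather than a recalled study result, but it should be stated as an assumption.
- *The executed list cannot be seen.* It sits in an external folder, a mapping starting from 427.31 alone might never have produced I48.92, and Appendix A adds a trailing x to many codes as shorthand. This stands. It limits the claim to the rule as printed. It does not remove the point, because this criterion prints its own ICD-10 list: if the executed list holds only I48.91, the printed specification is wrong; if it holds the wildcard, the cohort definition is.
- *The repeat-diagnosis rule screens most cases.* A patient with an isolated flutter code, or with enough fibrillation codes to qualify anyway, is unaffected. This also stands and narrows the group, but repeated I48.92 claims still satisfy the rule.
- *Both arms face the same rule.* After matching, the atrial fibrillation covariate is present in 97.3% of warfarin and 97.2% of rivaroxaban patients, and other cardiac dysrhythmia in 55.9% and 55.4%. This is reasonable support for a small effect, although the codes behind both covariates are not given.

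A reader might go further and infer that thousands of flutter patients were enrolled and that the hazard ratio is biased. The document supports neither inference. It has no count by code or coding era, the 2% to 8% range has no source, and nothing shows that flutter-only patients differ between the arms.

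**Conclusion.** The point holds for the specification as printed: inclusion 2 is closed to flutter under ICD-9 and open to unspecified flutter under ICD-10. That conflicts with the restriction in Section 5.1 and makes eligibility depend on coding era. It rests on the standard meaning of I48.91, I48.92 and 427.32, and on the printed list being the one that was run.

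The size is unknown. The matched-cohort range of roughly 850 to 3,400 illustrates an assumption and is not an estimate, and its upper end would be too high if the atrial fibrillation covariate excludes flutter. Neither the direction nor the size of an effect on the hazard ratio can be derived, and the effect is probably small. The point is worth correcting because it changes who may enter and the edit is specific. In this version the Section 13 entries and the Section 14 result tables are still blank.

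**What to change.** Replace I48.9x with I48.91 in inclusion 2 and in the executed code list. Check the executed list first. If it never contained I48.92, only the printed text needs correcting.

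If it did contain I48.92, count by arm and database the patients who qualify only through that code. Then re-run the Section 5.3 flowchart, the propensity-score match, Appendix B, and the follow-up, censoring, risk and power tables of Sections 9 and 10, before the comparative analysis.

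If flutter is meant to be eligible, make both eras agree by adding 427.32, I48.3x and I48.4x, and state the departure from the trial criterion.

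The cost is a small loss of patients, with little loss of power, and more than a single code edit: the balance and final power assessments, which Section 10 records as reviewed by the principal investigator and the FDA in September 2020, would have to be repeated and reviewed again.
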